#### 2.1.2 Successful Implant Population

The Successful Implant population includes all subjects who are enrolled in Phase 2 of the study with a successful implant of the Aveir LP device.

### 2.2 Statistical Methods

For the confirmatory endpoints of the study, hypothesis tests will be performed. In addition, a set of additional data will be summarized by descriptive statistics or Kaplan-Meier analysis.

#### 2.2.1 Descriptive Statistics for Continuous Variables

For continuous variables (e.g. age, etc.), results will be summarized with the numbers of observations, means, standard deviations, minimums and maximums. Two-sided 95% confidence intervals for the means may be presented as appropriate.

#### 2.2.2 Descriptive Statistics for Categorical Variables

For categorical variables (e.g. gender, cardiac disease history, etc.), results will be summarized with subject or observation counts and percentages/rates, etc. Two-sided exact 95% Clopper-Pearson confidence intervals may be presented as appropriate.

#### 2.2.3 Kaplan-Meier Analysis for Time-to-event Variables

## Statistical Analysis Plan

subjects with events the time to the first event will be used for the analysis. Survival estimates of the data and associated 95% confidence interval will be presented using cumulative survival and its estimated standard error (Greenwood's formula).

### 2.3 Endpoint Analysis

The confirmatory endpoint analyses will be based on the 210 newly enrolled subjects in the Phase 2 study only. Subjects who are replaced with the Aveir LP are not included in the confirmatory endpoint analysis.

#### 2.3.1 Confirmatory Safety Endpoint

The confirmatory safety endpoint evaluates the 12-month complication-free rate (CFR) based on CEC adjudication of the adverse event. Complication is defined as a device-or-procedure-related serious adverse event, including those that prevent initial implantation. This definition of complication is equivalent to the term SADE (Serious Adverse Device Effect) throughout this SAP. The CEC will make the final determination regarding whether an adverse event meets the criteria for the confirmatory endpoint analysis.

The confirmatory safety hypothesis at 12 months timepoint is:

$H_0$ : CFR  $\leq$  83% vs.  $H_1$ : CFR  $>$  83 %

where 83% is the performance goal.

[REDACTED]

[REDACTED]

SADE events that occur on or before the 12-month follow-up visit (360 days) will be included in the confirmatory safety endpoint analysis.

To eliminate the possible impact of Covid-19 on the confirmatory safety endpoint analysis, CEC adjudicated primary safety events (SADEs) that are related or possibly related to Covid-19 will be excluded from the confirmatory safety endpoint analysis. Subjects who have these events will be censored at the time of the event. Additional analysis with these events included will also be provided.

Additional sensitivity analysis based on all the enrolled subjects to assess the impact of missing data on the confirmatory safety endpoint will be performed and they are described in Section 2.8.

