3.2.1 Confirmatory Endpoints

3.2.1.1 Confirmatory Safety Endpoint

The goal of the confirmatory safety endpoint evaluation is to demonstrate an acceptable complication-free rate (CFR); including any complication that prevents initial implantation.

[REDACTED]

Confirmatory Safety Endpoint Evaluation at 12-months:

H_0 : CFR \leq 83% vs. H_1 : CFR $>$ 83%

[REDACTED]

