22.0 Appendix II: Definitions

Adverse Event: An adverse event (AE) is any untoward medical occurrence, unintended disease or injury, or untoward clinical signs (including abnormal laboratory findings) in subjects, users or other persons, whether or not related to the medical device under investigation.

As part of ISO14155 Section 3.2, the Adverse Event definition has the following notes:

Note 1: This definition includes events related to the medical device under investigation or the comparator.

Note 2: This definition includes events related to the procedures involved.

Note 3: For users or other persons, this definition is restricted to events related to medical devices under investigation.

Complication: A device- or procedure-related serious adverse event, including any adverse event that prevents initial implantation.

Cardiac Tamponade: Confirmed or suspected accumulation of fluid in the pericardial space.

Cardiac Perforation: An excursion of the LP through the cardiac muscle. Signs and symptoms of a perforation by LP may include radiographic evidence of excursion of the LP into the pericardial sac, abnormal echocardiography indicative of a perforation, the accumulation of fluid in the pericardium, cardiac tamponade, or subject symptoms such as chest pain and discomfort.

Device deficiency: Any inadequacy in the identity, quality, durability, reliability, safety or performance of an investigational device, including malfunction, use errors or inadequacy in information supplied by the manufacturer.

Device-malfunction: the failure of a device to meet its performance specifications or otherwise perform as intended. Performance specifications include all claims made in the labeling for the device. The intended performance of a device refers to the intended use for which the device is labeled or marketed.

Diaphragmatic/Phrenic Nerve Stimulation: Electrical activation of the diaphragm muscle by the device output pulse. The abrupt diaphragmatic contraction is noted clinically as hiccups associated with each pacing stimulus. The pacing stimulus may stimulate the diaphragm either directly or indirectly via the phrenic nerve.

Dislodgement: The movement of the LP from its originally implanted position resulting in elevated pacing thresholds or a decrease in sensing.

Clinical Investigation Plan for Europe

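### The SAP's confirmatory safety event is limited to serious events, while the protocol's definition, on its more natural reading, also counts a non-serious adverse event that prevents implantation

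*SAP*

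**What the plan says.** Protocol 22.0 (Appendix II: Definitions) defines a complication as: "A device- or procedure-related serious adverse event, including any adverse event that prevents initial implantation". Protocol 3.2.1.1 sets the endpoint as an acceptable CFR, "including any complication that prevents initial implantation", and so relies on that defined term.

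SAP 2.3.1 words it differently: "Complication is defined as a device-or-procedure-related serious adverse event, including those that prevent initial implantation". It continues: "This definition of complication is equivalent to the term SADE (Serious Adverse Device Effect) throughout this SAP". On which events enter the test, it says: "SADE events that occur on or before the 12-month follow-up visit (360 days) will be included in the confirmatory safety endpoint analysis". On adjudication, it says: "The CEC will make the final determination regarding whether an adverse event meets the criteria for the confirmatory endpoint analysis".

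The SAP abbreviation list (5.0) labels ADE as non-serious and lists SADE separately. SAP 2.1.1 counts a subject as enrolled once consent is signed and an implant is attempted, so failed implants belong to the enrolled population.

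**The concern.** The two documents describe different numerators for the same confirmatory endpoint. In the protocol, the clause on implant prevention refers to any adverse event. In the SAP, the word that replaces it points back to serious adverse events. The link to SADE and the day-360 sentence then carry the serious-only limit into the analysis.

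The gap is narrow: it is the set of non-serious adverse events that prevent initial implantation. The protocol leaves room for such events. Appendix II treats several procedural events (for example pericardial effusion or ventricular arrhythmia) as serious if they require or prolong hospitalization. Protocol 3.5.5.1 grades one kind of access-site haematoma as needing no intervention. An event of that kind could end a procedure without meeting a seriousness criterion.

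At stake is the direction of the difference. Dropping events from the numerator can raise the CFR and cannot lower it, so the SAP wording favours the device. If the texts stay unreconciled, the choice between them may be made after the events are known.

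**Working it through.** This is first a comparison of texts. The plan has no visible figure to reproduce, because the sample size, success rule and multiplicity text (SAP 2.4, 2.7, 2.10) is redacted.

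**Step 1: the texts side by side.**

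| Event during the implant attempt | Protocol Appendix II | SAP 2.3.1 |
|---|---|---|
| Related and serious, implant prevented | Complication | Event |
| Related and serious, implant not prevented | Complication | Event |
| Non-serious, implant prevented | Complication, on the more natural reading | Not an event |
| Non-serious, implant not prevented | Not a complication | Not an event |

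Only the third row differs.

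**Step 2: what happens to a third-row subject.** The subject is enrolled (SAP 2.1.1), followed for 30 days and withdrawn (Protocol 3.5.3.5). Under the SAP wording the subject adds no endpoint event.

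**Step 3: scale, under stated assumptions.** Inputs from the documents: n = 210 (SAP 2.3), and p0 = 0.83, "where 83% is the performance goal". Assumptions: an exact one-sample binomial test with no censoring, and one-sided alpha of 0.025 or 0.05.

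- Weight of one subject: 1/210 = 0.00476, or 0.48 points.
- Pass limit: the smallest r with P(X ≥ r | n = 210, p = 0.83) ≤ alpha.
- Alpha 0.025: r = 186, so at most 24 complications. 186/210 = 88.6%, exact lower bound 83.47%. With 25 complications the bound is 82.93% and the goal is missed. Attained level 1.6%.
- Alpha 0.05: r = 184, so at most 26 complications. 184/210 = 87.6%, exact lower bound 83.24%. With 27 the bound is 82.71% and the goal is missed. Attained level 4.1%.

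**Step 4: effect on the error rate.** Let d be the share of subjects whose only qualifying event is a non-serious one that prevented implantation. The documents give no value, so d is assumed over a range that starts at zero. If the protocol-defined CFR is exactly 83%, the chance of passing on the SAP definition is P(X ≥ r | n = 210, p = 0.83 + d).

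| d (subjects = 210 × d) | alpha 0.025, r = 186 | alpha 0.05, r = 184 |
|---|---|---|
| 0 | 1.6% | 4.1% |
| 0.5% (about 1) | 2.6% | 6.1% |
| 1% (about 2) | 3.9% | 8.8% |
| 2% (about 4) | 8.5% | 16.7% |
| 3% (about 6) | 16.5% | 28.8% |

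These figures show sensitivity only. SAP 2.3.1 censors subjects with Covid-19-related events and SAP 2.2.3 describes Kaplan-Meier estimates with Greenwood errors, so the actual test may be a time-to-event bound with a different limit.

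**The case against.** **Including may only name a subset.** In Appendix II the word normally introduces members of the class just named, here related serious events. On that reading the two documents agree, and the endpoint text in 3.2.1.1 adds no non-serious limb of its own. This is possible but weaker. A related serious event that prevents implantation already qualifies, so the clause would do no work, and a phrase covering any adverse event is odd wording for a subset. If the subset was meant, the protocol sentence needs correcting instead.

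**The SADE sentence is a labelling rule.** This stands in part: the SAP gives no separate definition, and the narrowing rests mainly on the change of wording in the definition. The label reinforces it, because the SAP's own abbreviations separate serious from non-serious device effects.

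**The CEC will decide.** It decides against the stated criteria, and the SAP's criterion is serious-only. The CEC charter is not in these documents, so what the committee would actually do cannot be established.

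**Such cases stay visible.** SAP 3.2 and 3.5 report all adverse events and the reasons for unsuccessful implants. That is useful, but those tables carry no test and do not repair the endpoint.

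**Stronger readings that the documents do not support.** A reader might infer that protocol-defined complications are in fact being lost, or that the CFR is overstated by several points. No rate is given, and many events that abort an implant may be serious because they prolong hospitalization. A reader might infer that a single event decides the trial at 24 versus 25. That boundary exists only under an assumed exact test at one-sided 0.025. A reader might also blame this wording for such subjects counting against neither confirmatory endpoint. The visible text does tie effectiveness to successful implants (SAP 2.9), but that exclusion applies under either definition of complication.

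**Conclusion.** The point holds as a mismatch of definitions between the two governing documents, on the confirmatory safety numerator and in the direction that favours the device. It rests on the more natural reading of Appendix II and on the visible text. Redacted passages in Protocol 3.2.1.1 and SAP 2.3.1 could bear on it.

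The practical size is unknown and may be nil. What can be said is 0.48 points per subject, with 24 or 26 complications as the most that pass under the two assumed alphas. The correction is worth making because it is cheap and settles the numerator in advance.

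**What to change.** In SAP 2.3.1, restore the Appendix II definition: "A device- or procedure-related serious adverse event, including any adverse event that prevents initial implantation". Call the endpoint event a complication throughout 2.3.1, including the day-360 and Covid-19 sentences, and remove the statement that complication and SADE are equivalent. Keep SADE, with its ordinary serious-only meaning stated, for the adverse event summaries in SAP 3.2, so that the term is not left undefined. Carry the same complication criterion into the CEC adjudication, so that a non-serious event that prevented implantation is identified.

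If the sponsor intended the narrower meaning, amend Appendix II instead, before the analysis. Either way, a plain statement of whether non-serious events that prevent implantation count would remove the remaining ambiguity.

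Cost: a few sentences and one adjudication item. The CFR may become slightly less favourable.

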## Statistical Analysis Plan

### 2.3.2 Confirmatory Effectiveness Endpoint

The confirmatory effectiveness endpoint is a 12-month composite success rate (Rate) evaluating pacing thresholds and R-wave amplitudes.

The confirmatory effectiveness hypothesis is:

$H_0$ : Rate  $\leq$  80% vs.  $H_1$ : Rate  $>$  80%

Where 80.0% is the effectiveness performance goal.

The Rate is the proportion of subjects who have met success criteria in the confirmatory effectiveness endpoint. The acceptable ranges for sensing and pacing which define success criteria are shown in the table below:

Parameter	Acceptable values
Pacing voltage	Pacing threshold $\leq$ 2.0 V at 0.4 ms
R Sensitivity	R-wave amplitude $\geq$ 5.0 mV or $\geq$ value at implant

Success Criteria: A subject will be considered to have met the confirmatory effectiveness endpoint if: pacing threshold voltage  $\leq$  2.0 V at 0.4 ms at 12-month visit **and** the sensed R-wave amplitude is either  $\geq$  5.0 mV at the 12-month visit or  $\geq$  the value at implant.

[REDACTED]

[REDACTED]

[REDACTED]

[REDACTED]

An additional analysis for confirmatory effectiveness endpoint will also be conducted for subjects in the successful implant population who complete the 12-month visit with evaluable device measurements available. [REDACTED]

[REDACTED]

## Statistical Analysis Plan

threshold only. These conditions/procedures result in infrequent or absent intrinsic R-waves and may include pacemaker dependence, complete heart block, or AV node/AV junctional ablation.

Additional sensitivity analysis will be performed on the successful implant subjects to assess the impact of missing data and they are described in Section 2.8.

### 2.3.3 Confirmatory Secondary Endpoint

The confirmatory secondary endpoint includes evaluation of CAEP exercise protocol. If both the confirmatory safety and confirmatory effectiveness endpoints are met, the following hypothesis will be hierarchically evaluated.

The confirmatory secondary CAEP endpoint hypothesis is:

$H_0$ : Mean Slope is Not Equivalent to 100%

$| \text{Slope} - 100\% | \geq \delta$

$H_1$ : Mean Slope is Equivalent to 100%

$| \text{Slope} - 100\% | < \delta$

Where,  $\delta$  = equivalence margin, equal to 35%

#### CAEP exercise protocol

All capable subjects who have completed the 6-minute walk test (6MWT) will be asked to perform a maximal effort CAEP exercise protocol to demonstrate an appropriate and proportional response of sensor-indicated rate in graded exercise tests.

Data from subjects who have completed the 6MWT and have completed at least stage 3 of the CAEP exercise protocol, or 3.6 metabolic equivalent of task (METs), will be included in the analysis. The results of subjects who did not meet the analysis criteria will still be reported.

The analysis of these exercise test data will provide an estimate of the slope of the normalized increase in sensor-indicated rate versus normalized CAEP workload for each subject.

**Statistical Analysis Plan**

- [REDACTED]  
[REDACTED]
- [REDACTED]  
[REDACTED]
- [REDACTED]

[REDACTED]

[REDACTED]  
[REDACTED]  
[REDACTED]

[REDACTED] [REDACTED] [REDACTED]

[REDACTED]  
[REDACTED]

[REDACTED]  
[REDACTED]

[REDACTED] [REDACTED]

[REDACTED]

[REDACTED]

[REDACTED] [REDACTED]

[REDACTED]

[REDACTED] [REDACTED] [REDACTED] [REDACTED]

[REDACTED]  
[REDACTED]

[REDACTED]  
[REDACTED]  
[REDACTED]

[REDACTED] [REDACTED]

[REDACTED]  
[REDACTED]

[REDACTED]  
[REDACTED]

[REDACTED]  
[REDACTED]

## Statistical Analysis Plan

### 2.4 Sample Size Calculations

[REDACTED]

[REDACTED]

[REDACTED]

[REDACTED]

### 2.5 Interim Analysis

[REDACTED]

### 2.6 Timing of Analysis

[REDACTED]

### 2.7 Study/Trial Success

[REDACTED]

### 2.8 Handling of Missing Data

[REDACTED]

[REDACTED]

## Statistical Analysis Plan

[REDACTED]

[REDACTED]

[REDACTED]

[REDACTED]

### 2.9 Poolability Issue

Poolability of the confirmatory safety endpoint on the enrolled subjects and confirmatory effectiveness endpoint on the successful implant subjects by region and across sites will be evaluated. Analysis will be performed based on available data.

The Phase 2 study will be conducted in up to 80 sites in the United States, Europe, Canada, and Australia. The study will be conducted following the same investigational plan, monitoring plan and training plan in all regions. [REDACTED]

[REDACTED]

[REDACTED]

[REDACTED]

[REDACTED]

## Statistical Analysis Plan

2.10 [REDACTED]  
[REDACTED]  
[REDACTED]2.11 [REDACTED]  
[REDACTED]  
[REDACTED]

### 3.0 DESCRIPTIVE ENDPOINTS AND ADDITIONAL DATA

#### 3.1 Baseline and Demographic Characteristics

The following baseline, demographic, medical history and medication variables will be summarized descriptively for the subjects in the enrolled population: gender, age, ethnicity, race, history of smoking; key cardiovascular history, prior cardiac interventions, arrhythmia history, primary indication for study device implant, use of beta blocker, ACE, ARB, anti-coagulation, anti-arrhythmic, and anti-platelet medications, etc. and as needed. For subjects enrolled from European sites, race and ethnicity are not collected and hence will not be included in race/ethnicity summary of the demographics table.

#### 3.2 Adverse Events

All reported adverse events (AE), serious adverse events (SAE), adverse device effects (ADE), serious adverse device effects (SADE), unanticipated adverse device effect (UADE) or unanticipated serious adverse device effect (USADE) will be summarized for all enrolled subjects using the number of events, the number of subjects with events and the percentage of subjects with events. All CEC adjudicated events will also be summarized for all enrolled subjects with the number of events, the number of subjects with events and the percentage of subjects with events. An AE listing which includes all adverse events and whether or not each event is device-related or procedure-related will be provided.

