3.1 Study Design and Scope

The Leadless II Study - Phase 2 is a prospective, non-randomized, multi-center, international clinical study designed to **confirm** the safety and effectiveness of the Aveir LP System in a subject population indicated for a VVI(R) pacemaker. Sponsor will conduct the study at up to 80 centers worldwide (70 centers in the US, Canada, and Australia that contributed enrollments to the Phase 1 IDE study and 10 centers in Europe that contributed enrollments in the Leadless Observational Study in Europe).

[REDACTED]

[REDACTED]

[REDACTED]

Clinical Investigation Plan for Europe

[REDACTED]

Enrollment in this clinical study is expected to take approximately 6 months. Subjects participating in this clinical study will be followed through at least 12 months. Sponsor anticipates the total duration of the study to be approximately 24 months. All eligible subjects will undergo implant attempt with an Aveir LP.

The following study evaluations will occur after implant:

- Pre-discharge assessment
- 2-week follow-up visit (in-office or clinic)
- 6-week follow-up visit (in-office or clinic)
- 3-month follow-up visit (in-office or clinic)
- 6-month follow-up visit (in-office or clinic)
- 12-month follow-up visit (in-office or clinic)
- Every 6 months thereafter until study completion

Follow-up schedules will be calculated from the date of successful implant.

The clinical investigation has been designed to involve as little pain, discomfort, fear, and any other foreseeable risk as possible for subjects. Refer to the Risks Analysis section of this clinical investigation plan for details.

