#### 2.1.1 Enrolled Population

The Enrolled population includes all subjects who are enrolled in Phase 2 of the study. Subjects who sign an IRB/EC-approved informed consent and have an attempted implant will be considered enrolled in the study.

An attempted implant is defined as the point of skin incision for the insertion of the Aveir Introducer (LSN25301 or LSN25501) for the implant procedure.

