## Statistical Analysis Plan

- Remaining device longevity at the six-month visit, as displayed by the programmer based on delivered therapy, programmed settings, percent pacing, and measured pacing impedance
- Average pacing rate, impedance, pulse amplitude, pulse duration and percentage pacing will also be reported for all visits.
- Hospitalizations
- Mortality

These additional data will be summarized descriptively using the methodology as outlined in Section 2.2 Statistical Methods in the SAP, based on subjects in the enrolled and/or successful implant population with available data as appropriate. No hypothesis tests will be performed.

Subjects with a Nanostim SR device who are replaced with the Aveir LP device will not be in the confirmatory endpoint analysis population. For these subjects, LP device replacement success rates, data summaries and/or listings for all adverse events and device measurements, from the time of LP replacement through their last available follow-up, will be provided.

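### SAP 3.2 reports adverse events as crude percentages with no onset window, so they depend on entry date and data cut and are not 12-month risks

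*SAP*

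**What the plan says.** SAP 3.2 summarises every class of reported event for all enrolled subjects "using the number of events, the number of subjects with events and the percentage of subjects with events". It applies the same three statistics to CEC-adjudicated events and adds an event listing. It names no onset cut-off, no patient-time and no Kaplan-Meier estimate, and nothing in the section is redacted. The denominator comes from SAP 2.1.1: "Subjects who sign an IRB/EC-approved informed consent and have an attempted implant will be considered enrolled in the study".

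Follow-up is set out in Protocol 3.1:

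- Accrual: "Enrollment in this clinical study is expected to take approximately 6 months"
- Minimum follow-up: "Subjects participating in this clinical study will be followed through at least 12 months"
- Visits then continue: "Every 6 months thereafter until study completion"
- Overall length: "Sponsor anticipates the total duration of the study to be approximately 24 months"

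Protocol 3.5.5.6 has adverse events assessed at the 12-month visit and at each later visit. Subjects with an unsuccessful implant (Protocol 3.5.3.5), or with a device removed and no replacement Aveir LP (Protocol 3.5.4), are followed for 30 days and then withdrawn.

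The confirmatory safety endpoint does have a window. SAP 2.3.1 states: "SADE events that occur on or before the 12-month follow-up visit (360 days) will be included". The same section treats complication and SADE as one term throughout the SAP. SAP 2.2 permits Kaplan-Meier for additional data, and 2.2.3 describes it with a 95% confidence interval. For subjects moved from a Nanostim device, SAP 3.5 states the period covered: "from the time of LP replacement through their last available follow-up".

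**The concern.** A percentage of subjects with an event has a clear meaning only when the time at risk is stated. Here each subject contributes whatever follow-up has accrued by the data cut. Two reports on the same device, cut six months apart, would show different percentages with no change in risk.

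The trial's stated objective runs from implant through 12 months, and the complication-free rate is cut at day 360. Because the SAP equates complication with SADE, a reader will naturally set the SADE percentage from 3.2 beside one minus the complication-free rate. The two cover different periods, and nothing in 3.2 warns of this.

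**Working it through.** The documents give no adverse event percentage, so there is no figure of the plan's to reproduce. The check asks what a crude percentage would show for an assumed 12-month risk r.

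**Inputs from the documents.** Enrolment about 6 months, minimum follow-up 12 months, total duration about 24 months (Protocol 3.1); 30-day exits (Protocol 3.5.3.5 and 3.5.4).

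**Assumptions.** Uniform enrolment; the values of r; the timing of events; the two data cuts; day 360 treated as month 12.

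**Step 1: follow-up at each cut.** Follow-up is the cut minus the entry time, with entry between month 0 and month 6.

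- Cut when the last subject reaches month 12 (study month 6 + 12 = 18): 18 − 6 = 12 to 18 months.
- Cut at study month 24: 24 − 6 = 18 to 24 months.

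Each cut gives a 6-month spread, apart from early exits.

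**Step 2: constant hazard.** The monthly hazard is h = −ln(1 − r)/12. The mean crude percentage over follow-up from a to b is 1 − [exp(−ha) − exp(−hb)]/[h(b − a)]. For r = 20%, h = 0.2231/12 = 0.01860 and 6h = 0.1116.

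- 12 to 18 months: 1 − (0.8000 − 0.7155)/0.1116 = 24.3%.
- 18 to 24 months: 1 − (0.7155 − 0.6400)/0.1116 = 32.3%.

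**Step 3: events concentrated near implant.** Two front-loaded shapes were used, each with a constant hazard afterwards.

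- Half of the 12-month risk in month 1. For r = 20% the later hazard is ln(0.9/0.8)/11 = 0.01071 per month.
- 80% of the 12-month cumulative hazard in the first 1.5 months. For r = 20% the later hazard is 0.2 × 0.2231/10.5 = 0.00425 per month.

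| 12-month risk | Event timing | Cut at month 18 | Cut at month 24 |
|---|---|---|---|
| 20% | constant | 24.3% | 32.3% |
| 20% | half the risk in month 1 | 22.5% | 27.3% |
| 20% | 80% of hazard in 1.5 months | 21.0% | 23.0% |
| 10% | constant | 12.3% | 16.8% |
| 10% | 80% of hazard in 1.5 months | 10.5% | 11.6% |
| 5% | constant | 6.2% | 8.6% |
| 5% | 80% of hazard in 1.5 months | 5.3% | 5.8% |

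**Step 4: early exits.** These pull the other way. Suppose 5% of subjects have only 1 month of follow-up, with r = 20% and a constant hazard. The 1-month risk is 1 − 0.8^(1/12) = 1.8%.

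- Month 18: 0.95 × 24.3% + 0.05 × 1.8% = 23.2%.
- Month 24: 0.95 × 32.3% + 0.05 × 1.8% = 30.8%.

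**Step 5: a day-360 window.** If every subject is followed to day 360, the expected percentage equals r, whatever the cut. With the 5% of early exits it is 0.95 × 20% + 0.05 × 1.8% = 19.1%. The window removes the dependence on the cut; a censoring-adjusted estimate is still needed for the exits.

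**The case against.** **Redaction.** SAP 2.5 to 2.8, including the timing of analysis and missing data, are redacted, and the opening of 2.2.3 is missing from the available text. The cut may be fixed there, so its absence cannot be claimed. That stands. However, a calendar cut alone would not equalise follow-up, because subjects enter over about 6 months. Only a per-subject limit would, and 3.2 neither states one nor refers to one.

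**Ordinary practice.** Counts and percentages are usual for descriptive safety tables, there is no control arm whose comparison could be biased, and 3.2 never calls its figures 12-month rates. All true. The point concerns how the tables can be read; it is not a mislabelling.

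**The SADE table and the complication-free rate differ anyway.** SAP 2.3.1 censors Covid-related SADEs from the main analysis. That also stands, but 2.3.1 plans a further analysis with those events included, and a day-360 SADE table could be set beside it.

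**Size.** No event risk or hazard is given in the documents. Many foreseeable events listed in Protocol 6.0 belong to the procedure, and Protocol 10.2 says the electrode interface typically matures by three months. With front-loaded timing the excess is small. This stands for device and procedure events; all-cause adverse events need not follow that pattern.

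**Stronger readings that the documents do not support.**

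- A reader might infer that follow-up ranges over 12 to 24 months in one table. That joins two alternative cuts.
- A reader might treat these tables as the whole safety picture. The complication-free rate, the event listing, mortality, hospitalizations and early terminations are also reported.
- A reader might infer a distorted comparison between the Nanostim replacement subjects and the newly implanted subjects. SAP 3.5 plans no such comparison, and the continued-access appendix is largely redacted, so the replacement group's follow-up cannot be judged.

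**Conclusion.** The point holds for the descriptive tables. As written, the SAP 3.2 percentages accumulate to the data cut over unequal follow-up. They rise with earlier enrolment and a later cut, and they cannot be read as 12-month risks. The SADE percentage does not share the day-360 period of the complication-free rate.

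For a true 12-month risk of 20%, the crude figure would be about 21 to 24% at study month 18 and 23 to 32% at month 24, an excess of roughly 1 to 12 percentage points. The lower end applies if events cluster at implant, the upper end if the hazard is constant. These figures rest on assumed risks, hazard shapes, uniform enrolment and cut dates, and they leave out early exits, which lower them.

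A reader might infer that the confirmatory safety conclusion is at risk. It is not: that analysis is already limited to 360 days. This is a cheap improvement to descriptive reporting.

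**What to change.** In SAP 3.2:

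- Tabulate AEs, SAEs, ADEs and SADEs, reported and CEC-adjudicated, with onset through day 360, using the cut in 2.3.1.
- For subjects with at least one event, give the Kaplan-Meier percentage at day 360 and its 95% confidence interval by the method of 2.2.3, so that 30-day exits and other losses are handled as censored.
- Show events after day 360, or over all available follow-up, in a separate table with patient-years of exposure.
- For the Nanostim replacement subjects in SAP 3.5, state the follow-up time alongside their adverse event summaries. No time-matched comparison is needed.

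The cost is SAP wording and a few extra table columns. Event onset dates are already collected (Protocol 6.0); the last-contact date is the only other item needed. The confirmatory analyses do not change.
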